10. RESEARCH INFORMATION IN MEDICAL RECORDS

No information from this research will be included in the participants' medical records.

11. DATA ANALYSIS AND MONITORING

Sample Size Determination

We will target 40 participants (20 women, 20 men)for the reason that some statistical power is expected while we also are aiming to keep the study size appropriate for the logistics of recruiting and retention of subjects for both trials. We aim to recruit and consent 46 participant (23 women, 23 men) in anticipation of some drop out. A

complete cohort of 20 women and 20 men will afford the opportunity to assess sex-based differences. We have performed power analysis on the pairwise correlations between k_{el} and MeHg demethylation rate and/or bacterial taxa abundance. With grouped sexes, 40 subjects will have at least 80% power to detect a linear relationship where 19% or more of the variance in elimination rate is explained by de-methylation status or particular bacterial species abundance.

Planned Statistical Analysis

Relationships of taxa abundance with kinetic parameters of MeHg elimination rate (k_{el}), biotransformation in vivo (B_{vivo} , %iHg in feces) and in vitro (B_{vitro} , %MeHg biotransformation in cultures) will be evaluated. A total of 117 numerical values for k_{el} and B_{vivo} , B_{vitro} will be available (37 from our prior study and 40 subjects X 2 trials in the present study). Evaluation of slopes and R^2 values for elimination rate calculations in the prior study demonstrates that a difference of two days in MeHg half-life between two subjects can be determined with significance. Pairwise t-tests will be used to assess significance among pre- vs. post-prebiotic elimination rates (Aim1). The correlation between the (k_{el}) and biotransformation (B_{vivo} and B_{vitro}) will be evaluated for the 40 X 2 = 80 new human subject determinations in Aim 1. Graphical and numerical diagnostics will be used to test the linearity of the relationships and the homogeneity of variance. If these conditions are met, linear regression will be used to estimate functions for predicting k_{el} from B_{vivo} or B_{vitro} . The R system for statistical computing will be used throughout [26].

Data and Safety Monitoring.

All records with information identifying a study subject will be kept in a secure, locked office or on a secure computer at the U of R site. Only the P.I. will have access to these records. All samples will be coded so as to remove any subject specific information. The laboratory staff will only have access to subject samples and various non-identifying analytical parameters. Samples shared with co-investigators at Montana State University (MSU) will be de-identified. In addition, the PI will consult with the MSU Co-Is to advise on practices of avoiding any possible disclosure of subject's personal information. In accordance with regulations, we may share a copy of the consent form and records that identify individual subjects with the U of R, MSU Department of Health and Human Services and National Institutes of Health.

12. OVERSIGHT PLAN. As PI, [name] will provide administrative and scientific oversight for all activities carried out by co-investigators [name] and [name] at Montana State University. The PI will be responsible for conducting monthly meetings via Zoom or telephone to review study activities. Ongoing training of staff will be implemented to ensure protocol compliance. Data analysis will be reviewed on a monthly basis. In instances where there is a breach of privacy/confidentiality it will be promptly reported to the PI. Additional oversight and review of data analysis will occur at an annual meeting where PI, co-Is and students and staff members of the study will physically convene in either Rochester or Bozeman Montana.

13. FOLLOW UP COMMUNICATIONS. The Study PI will not initiate unsolicited contact with subjects but subjects may contact the Study PI to inquire about study status and

results subsequent to completing their study activities. It is anticipated subjects will contact the Study PI via email, at which point the Study PI will call the subject by phone to review an information sheet delineating the risks and conditions of communication via email, and proceed to obtain verbal consent for using email. The timeframe within which the Study PI will receive and respond to email inquiries will be through August 31st of 2023, when the project funding is anticipated to expire, and study results will be complete. Information about the study that is anticipated to be shared with subjects includes aggregate results and individual results specific to the subject only. Prior to sharing any data, the PI will confirm the subject data set matches the subject identity via a cross reference to the assigned alpha-numeric identifier assigned and recorded on the consent form as detailed in section 5C above. In addition, the Study PI, when requested by the subject, will inform the subject of published results and, where allowed by the publisher guidelines, share such document(s) via an electronic file (e.g. PDF file), or refer the subject to a publicly available site to access the publication.

REFERENCES

1. Clarkson, T.W., L. Magos, and G.J. Myers, *Human exposure to Mercury: Three Modern Dilemmas*. J. Trace Elements in Exp. Med., 2003. **16**: p. 321-343.
2. Hibbeln, J.R., et al., *Maternal seafood consumption in pregnancy and neurodevelopmental outcomes in childhood (ALSPAC study): an observational cohort study*. Lancet, 2007. **369**(9561): p. 578-85.
3. Budtz-Jorgensen, E., P. Grandjean, and P. Weihe, *Separation of Risks and Benefits of Seafood Intake*. Env. Health Persp., 2007. **115**: p. 323-327.
4. Kershaw, T.G., T.W. Clarkson, and P.H. Dhahir, *The relationship between blood levels and dose of methylmercury in man*. Arch Environ Health, 1980. **35**(1): p. 28-36.
5. Aberg, B., et al., *Metabolism of methyl mercury (203Hg) compounds in man*. Arch Environ Health, 1969. **19**(4): p. 478-84.
6. Miettinen, J.K., et al., *Elimination of 203Hg-methylmercury in man*. Annals of clinical research, 1971. **3**(2): p. 116-22.
7. Smith, J.C., et al., *The kinetics of intravenously administered methyl mercury in man*. Toxicol Appl Pharmacol, 1994. **128**(2): p. 251-6.
8. Al-Shahristani, H. and K.M. Shibab, *Variation of biological half-life of methylmercury in man*. Arch Environ Health, 1974. **28**: p. 342-344.

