Our scientific premise is that symbiotic microbes in the human gut are required for the efficient biotransformation and excretion of toxic MeHg. There is substantial evidence, including our own, that the rate of MeHg elimination in the human body relies on gut microbiota. Importantly, we discovered that MeHg elimination kinetics in an individual can vary significantly over time and, furthermore, is significantly slowed when taking antibiotics [10, 11]. Our initial findings with microbiome characterization yielded logical candidate bacterial taxa that now require validation to test their role in MeHg elimination [19]. With this evidence, we **hypothesize that a susceptibility for reaching harmful levels of MeHg in the body is dictated by select members of the human gut microbiome that: a) carry out MeHg demethylation to enhance excretion, b) are variably present or variably abundant between and within individuals over time and c) are metabolically responsive to diet supplementation.** Our Specific Aims are:

Aim 1. Establish gut microbiome samples that exhibit “fast” and “slow” MeHg kinetics in humans.

Aim 2. Validate the microbiome’s role in MeHg kinetics using germ-free/gnotobiotic mouse modeling.

Aim 3. Identify and isolate microbial species responsible for MeHg demethylation in the human gut.

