2. STUDY DESIGN

2A. Overview

Study site: This study will involve human subjects recruited from the greater Rochester area and will be conducted in the URMC Department of Environmental Medicine. Hg analyses and DNA extraction of fecal samples will be performed in the U of R Environmental Health Science Center (EHSC) Elemental Analysis Facility. Fecal samples will also be evaluated for MeHg demethylation activity by assaying bacterial enzyme activity in Rochester. Hg analyses of hair samples by LA-ICP-MS will be done at the Trace Element Analysis lab at Dartmouth College, New Hampshire. Additional studies, exempt from IRB approval, will be done at Montana State University with de-identified samples of human feces and fecal DNA that are shipped to co-investigators [name] and [name] at MSU.

Protocol: Subjects will follow a protocol of eating three fish meals within a two-week period to incur exposure to naturally occurring levels of MeHg in the fish. Fish meals will consist of 6-12 ounces of commercially available tuna steaks. This will be followed by an elimination period of 60 days where no fish or seafood is to be consumed. Single hairs collected at 60 days after the last of the three fish meals will be used to determine a MeHg elimination rate using LA-ICP-MS to perform longitudinal Hg elemental analysis as we have previously reported [10]. De-methylation of MeHg coming from the fish will be determined by direct analysis of iHg and MeHg in fecal samples collected

approximately four weeks following the final fish meal. Fecal samples will also be used for culture assays and for direct iHg/MeHg analysis to determine of MeHg demethylation rates *in vitro* and *in vivo*, respectively (Biotransformation, $B_{in\ vitro}$ and $B_{in\ vivo}$). Fecal DNA will be used for metagenomic analyses to profile type and abundance of all bacterial species present. Statistical correlations between elimination rate, demethylation rate and abundance of bacteria will be used to deduce strains of bacteria that contribute to demethylation and overall metabolism and elimination of MeHg. The above protocol will be performed in two separate “trials” (which are denoted as “Study Periods” to the

[figure not shown]

Figure 1. Protocol Overview.
Elimination rate determination, k_{el} ;
Demethylation (Biotransformation)
analysis, $B_{in\ vitro}$ and $B_{in\ vivo}$.

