participants in the consent form) within the course of approximately 10 months and separated by an intermediate “washout” period of 4 months (Figure 1). Subject will not be required to refrain from fish or seafood during this washout period. Prior to the second trial subjects will receive a commercially available over the counter prebiotic (Prebiotin™) to be orally self-administered on a regular schedule for the entire trial 2 period. This prebiotic is not the subject of this investigation in this study, and is simply selected for its known effects of shifting gut microbial composition to enrich for healthier strains of bacteria (e.g. Bifidobacteria). Fecal sampling prior to and subsequent to prebiotic will be used to document changes in the microbiota for each individual. The prediction is that prebiotic induced change in the gut microbiota will result in a change in MeHg metabolism kinetics in each

individual.

2B. Rationale for Study Design

The main rationale for this study design is based on our evidence that de-methylation of MeHg in the human gut is the driving force for faster elimination MeHg that comes with eating fish. We therefore predict that with the methods we now have available to measure MeHg kinetics, coupled that with high-resolution analyses of gut microbiome characteristics in individual people who have undergone a controlled exposure to MeHg, we can resolve a microbial basis for MeHg metabolism in humans. This is an ambitious undertaking, and hence, is designed as a consortium project to be executed by three investigators with respective expertise in 1) human MeHg kinetics, 2) mouse microbiome manipulations and 3) microbial metagenomics and culturing methods. By design, the human subject component of the study is to be carried out at URMC. The objective is to capture “slow” and “fast” MeHg metabolizing human microbiome samples, that can be handed off to colleagues at MSU for specialized analyses that do not involve the human subjects, simply their de-identified samples.

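### Section 11 states no subject or trial term for 80 paired values and no error control for the taxa screen, and its 80% power figure holds for one test only

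*Combined protocol and SAP*

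**What the plan says.** Under Sample Size Determination, section 11 makes one power statement for pairwise correlations: "40 subjects will have at least 80% power to detect a linear relationship where 19% or more of the variance in elimination rate". The second half of the sentence names two kinds of predictor, saying that this variance "is explained by de-methylation status or particular bacterial species abundance". Neither alpha nor sidedness is given.

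Under Planned Statistical Analysis, taxa abundance is to be related to three parameters: k_el, B_vivo and B_vitro. The values described as available number 117: "37 from our prior study and 40 subjects X 2 trials in the present study". The correlation of k_el with B_vivo and B_vitro "will be evaluated for the 40 X 2 = 80 new human subject determinations in Aim 1", followed by linear regression if linearity and homogeneity of variance hold. Those are the only conditions named. Pairing appears only in the t-tests of elimination rate before and after prebiotic.

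Section 2A sets the scope of the screen: "Fecal DNA will be used for metagenomic analyses to profile type and abundance of all bacterial species present". It adds that correlations among elimination rate, demethylation and abundance "will be used to deduce strains of bacteria that contribute to demethylation". The same section says of trial 2, which is run on prebiotic: "The prediction is that prebiotic induced change in the gut microbiota will result in a change in MeHg metabolism kinetics".

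**The concern.** Three gaps affect how the results can be read.

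- **Pairing.** Two values from one person are likely to resemble each other. Ordinary correlation and regression on 80 values assume that they do not, so p-values come out too small and confidence intervals for the slope too narrow.
- **Trial.** Trial and prebiotic coincide. If the prebiotic shifts both variables, pooling the trials produces a correlation even when none exists within either trial. The pooled coefficient then mixes two different things.
- **Multiplicity.** Testing every species against three parameters at an unadjusted 5% declares 5% of the unrelated species for each parameter. The power sentence names species abundance alongside demethylation, which invites the reader to apply the 80% to that screen.

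At stake are the strength of evidence for the k_el-demethylation relation and the list of strains taken forward to the mouse and culture work.

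**Working it through.** **1. The plan's own figure.** Inputs from section 11: n = 40, R² = 0.19. Assumed: alpha 0.05, two-sided.

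- r = √0.19 = 0.436 and Fisher z = atanh(0.436) = 0.467.
- z·√(n − 3) = 0.467 × √37 = 2.842.
- Power = Φ(2.842 − 1.960) = Φ(0.882) = 81.1%.

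The R² that gives exactly 80% is 0.185, which rounds to the stated 19%. A one-sided 5% test would give 88.4%, a poorer fit. The figure reproduces for a single two-sided test.

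**2. The same figure with more than one test (Bonferroni, n = 40, R² = 0.19).**

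| Tests | Critical value | Power |
|---|---|---|
| 1 | 1.960 | Φ(0.882) = 81% |
| 2 (k_el with B_vivo and with B_vitro) | 2.241 | Φ(0.600) = 73% |
| 3 (one species, three parameters) | 2.394 | Φ(0.448) = 67% |
| 10 | 2.807 | Φ(0.035) = 51% |

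No assumption about the number of taxa is needed here. With no adjustment, an assumed 100-300 unrelated taxa give 0.05 × 100 = 5 to 0.05 × 300 = 15 chance hits per parameter.

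**3. Eighty values treated as independent.** Let both variables have intraclass correlation ρ across the two trials. The documents give no value, so 0.3-0.7 is assumed. With no true association, the variance of the correlation is inflated by 1 + ρ², and the true error is 2·[1 − Φ(1.96/√(1 + ρ²))].

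| ρ | 1.96/√(1 + ρ²) | True error | Effective N = 80/(1 + ρ²) |
|---|---|---|---|
| 0.3 | 1.877 | 6.0% | 73 |
| 0.5 | 1.753 | 8.0% | 64 |
| 0.7 | 1.606 | 10.8% | 54 |

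Simulation of 40 people with two values each agrees: 6.0, 7.9 and 10.8%. Coverage of the nominal 95% confidence interval for the slope is about 94, 92 and 89%. A 95% prediction interval for a new person covers about 94-95%, because residual variance dominates its width and pairing hardly biases that.

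**4. A trial 2 shift in both variables.** Let each move by d SD (assumed 0.5-0.8), with no association within a trial. The pooled correlation is (d²/4)/(1 + d²/4).

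- d = 0.5: 0.0625/1.0625 = 0.059.
- d = 0.8: 0.16/1.16 = 0.138.

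With 80 values and ρ of 0.3-0.7, simulation gives rejection rates of about 9-13% at 0.5 SD and 24-27% at 0.8 SD. A subject random intercept without a trial term does not cure this; it rejects in 11-80% of runs over the same settings. Adding the trial term brings the rate to 5-6%.

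**The case against.** The strongest reply is that this is exploratory work. Section 3C calls the study a pilot, and section 11 expects only some statistical power. Section 1D mentions candidate taxa from earlier work and plans to validate the microbiome's "role in MeHg kinetics using germ-free/gnotobiotic mouse modeling" and then to isolate species. Chance hits would therefore meet an experimental check. That limits the harm, but it gives the screen no error rate. The candidate taxa are not named, and nothing restricts the screen to them.

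A second reply is that the trial term is partly a choice of estimand. Section 2A predicts that the microbiota change produces the kinetic change, so a shared shift may be the effect sought, and adjustment removes it. The t-tests recover the shift in k_el but not its link to a taxon. This stands: the 9-27% counts rejections without a within-trial association, and a reader should not infer that every such rejection is a false discovery. It is a reason to report both models, not to leave the choice unstated.

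Third, lost power is recoverable. Under Benjamini-Hochberg (assumed 100-300 taxa, 1-5 truly associated, q 5-10%), power at R² = 0.19 is 16-45% on 40 subjects. It is 63-90% on 80 values with pairing handled, or 41-75% if the association lies mainly between subjects. That also stands, but the stated figure does not rest on those values.

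**Conclusion.** The point holds as a gap in the analysis plan that gives wrong error rates if section 11 is followed as written. Ignoring pairing takes 5% to about 6-11%; a prebiotic shift in both variables takes it to about 9-27%. These sizes rest on assumed intraclass correlations of 0.3-0.7 and assumed shifts of 0.5-0.8 SD. The absence of a subject term, a trial term and a multiplicity rule rests on no assumption, and the 73%, 67% and 51% figures need only the 5% two-sided level.

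Four stronger readings are not supported:

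- The power figure is not an arithmetic error; it reproduces for one test.
- It does not count the 80 values as independent, since it is stated for 40 subjects.
- Prediction of k_el for a new person is not made falsely precise; the interval that fails is the one for the slope.
- A taxa analysis on all 117 values is an inference. Section 11 says only that those values will be available.

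**What to change.** 1. State alpha and sidedness. Name one k_el-demethylation test, with B_vivo or B_vitro, as the test that the 80%/19% sentence refers to. Remove taxa from that sentence, or restate their detectable R² for the number of tests and values actually used.
2. For taxa, apply Benjamini-Hochberg at a stated q after a prevalence filter fixed in advance. Define the family: k_el as the primary parameter, or all taxa-by-parameter tests together.
3. Analyse the paired values with a subject random intercept and a fixed trial (prebiotic) term as the main estimate of the within-trial association. Report the model without the trial term alongside it, since a microbiota-mediated shift is part of the hypothesis.
4. If the 37 prior values are pooled with the 80, add a study term and say whether any person contributes to both.

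The cost is SAP wording and a few lines in R, which the plan already uses. The price is fewer declared taxa, slightly wider intervals, and a less favourable detectable R² for taxa on the 40-subject basis.

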Prebiotic administration. Prebiotin™ (oligosaccharide enriched inulin), a commercially available prebiotic supplement from Jackson GI Medical (<https://www.prebiotin.com/about-us/>), will be distributed to the subjects for self-administration subsequent to the first trial and washout period and prior to the second trial (Figure 1). An intended use for Prebiotin™ is not the subject of investigation in this study. Prebiotic supplementation with this lawfully marketed over-the-counter dietary supplement is being used for its known properties of changing gut microbiome composition. Regarding FDA approval, use of Prebiotin™ in this study will be IND exempt in that all six (6) of the conditions under section 7.1 of Policy 605 of the Office of Human Subject Protection at the Univ. of Rochester are met. Briefly, with respect to Prebiotin™, this study: is not intended to support a new indication for use (7.1.1); is not intended to support a significant change in the advertising of Prebiotin™ (7.1.2); does not involve a change in route of administration, dosage level, or population at risk (7.1.3); will be conducted in compliance with the IRB review (7.1.4); will be conducted in compliance with requirements concerning the promotion and sale of Prebiotin™ (7.1.5); and, does not intend to request exception from informed consent requirements for emergency use (7.1.6). Individually packaged portions (4 grams) of the Prebiotin™ Prebiotic Fiber Stick Pac will be provided to subjects (<https://prebiotin.net/collections/our-products/products/prebiotin-prebiotic-fiber-stick-pac-4g>). Prebiotin™ is the prebiotic of choice in several published studies on gut microbiota control of obesity [20-22] and has been used in an NIH study on reducing inflammation in kidney patients [23]. For this study, we are targeting a dose of 8 grams/day. This dose amount is based on published effects of inulin on gut microbiota in the range of 4 to 16grams/day dosages [20, 24]. We have selected 8 grams/day based on the finding of Holscher et al [24], who demonstrated clear effects on shifting the microbiota composition and activity at the 7.5 gram/day dose level in healthy adults in a controlled double-blinded study. Prebiotin™ self-administration will be initiated one week prior to fish consumption in the second trial and extend through the entirety of the second trial (i.e. 11 weeks, Figure 1). Subjects will be given a 11-week supply of Prebiotin™ Stick Pacs and instructed on how to self-administer on either a once or twice daily dosing schedule. For the first week, subjects will be instructed to begin with a daily supplement of one Pac (4grams) a day, taken with meals. Starting the second week, and additional

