Fecal sample collection, DNA isolation and shipping. Feces will be used to capture the profile of the gut microbiota for each subject. Collection methods will therefore be aimed at capturing and preserving anaerobic species. At the initial visit, subjects will also be provided with instructions on the stool sampling protocol and provided with an easy to use commercially available collection container (Fisherbrand Commode Specimen Collection System) and an Omnipore-Gut collection tube for DNA subsampling (below). Stools will be sampled at three time points as indicated in Figure 1: approximately four weeks after the 3rd fish meal (for each trial) and at approximately one week prior to the 2nd Trial, preceding or contemporaneously with prebiotic supplementation (e.g. day 44 of the Trial 1 and day -7 and 44 of Trial 2). Collection of stools within 2-3 days centered on these target collection times will be acceptable. For all fecal samplings, the whole stool will be collected and frozen within 30 minutes to preserve microbe viability [25]. To stabilize a sample of the fecal DNA at the time of stool collection, a sub-sampling of feces with the Omnipore-Gut collection kit (DNA Genotek, Ottawa, ON, Canada) will be done by the subject according to the provided instructions. Subjects will be instructed to triple contain the stool collection with freezer-grade zip-lock bags provided. Subjects will ship the stool sample and the DNA stabilized sample to the P.I.'s lab using express shipping (FedEx) as soon as possible using the freezer packs and Thermosafe styrofoam packaging provided (see above). Alternatively, sample pick up by lab staff will be arranged. Fecal samples will be logged-in and coded for identity protection in the P.I.'s laboratory and kept frozen until analysis and DNA isolation. Fecal DNA will be isolated with the ZR fecal prep kit (Zymo Research) in the [name] lab and will be distributed to the [name] lab at MSU. Samples of feces will also be distributed to the [name] lab at MSU. Human feces falls under the "exempt human/animal specimens" category for shipping. A portion of frozen stool for each subject will be prepared in appropriate triple-layer packaging and containment (http://www.fedex.com/us/packaging/guides/Clinical_fxcom.pdf) and marked appropriately with "exempt human specimens" for shipping to MSU.

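### If paired, the pre/post-prebiotic t-test gives only a mean Trial 2 minus Trial 1 change in k_el, and no analysis is specified linking a person's change in microbiota or demethylation to their change in k_el

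*Combined protocol and SAP*

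**What the plan says.** Every subject completes two trials separated by a four-month washout. The prebiotic belongs to the second trial only: Section 5C says that "self-administration will be initiated one week prior to fish consumption in the second trial", and the schedule in Appendix 1 agrees. Hair is taken at the end of each trial, and Section 11 counts one set of kinetic values per subject per trial. Stools are collected at "day 44 of the Trial 1 and day -7 and 44 of Trial 2" (Section 5C).

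Section 2A states the expectation at the level of the person: "The prediction is that prebiotic induced change in the gut microbiota will result in a change in MeHg metabolism kinetics in each" individual. It adds that stool sampling before and after the prebiotic "will be used to document changes in the microbiota for each individual".

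Section 11 names these analyses:
- For the prebiotic: "Pairwise t-tests will be used to assess significance among pre- vs. post-prebiotic elimination rates".
- The correlation between k_el and biotransformation (B_vivo, B_vitro), which "will be evaluated for the 40 X 2 = 80 new human subject determinations".
- Linear regression to predict k_el from B_vivo or B_vitro, if diagnostics allow.
- Relationships of taxa abundance with the kinetic parameters, with no model or unit of analysis given.

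No change score, subject term or repeated-measures model appears there or in the shorter descriptions in Sections 2A and 5B.

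**The concern.** The prediction is about change within a person, but the named analyses address something else. A mean difference between trials says whether k_el moved on average. It does not say why, or whether the people whose microbiota moved most are those whose k_el moved most. A significant mean change could be read as a prebiotic effect although trial and prebiotic coincide completely for k_el. A null mean change could be read as refuting the per-person prediction although individual changes in opposite directions may cancel. A significant 80-value correlation could be read as support for the within-person link although stable differences between people can produce it.

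This bears on hypothesis (c) in Section 1D and on secondary objective 2 in Section 1B, both of which concern diet supplementation. The t-test is the only named comparison of k_el before and after the prebiotic.

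**Working it through.** **Inputs.** From Section 11: 40 subjects, two trials, 80 values, at least 80% power when 19% of the variance in elimination rate is explained. Assumed, because the documents do not give them: two-sided 5% level, ICCs, size of any shift shared between trials. SD below means the SD of the within-person difference in k_el.

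**1. The plan's own power figure.** Fisher z: power = Φ(atanh(√0.19) × √(40 − 3) − 1.96) = Φ(0.467 × 6.083 − 1.96) = Φ(0.88) = 81%. The stated figure reproduces for one value pair per person and one predictor.

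**2. What the paired t-test detects.** Noncentral t, n = 40, 39 degrees of freedom, noncentrality d × √40:

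| Mean change, any cause | Chance of significance |
|---|---|
| 0.1 SD | 9% |
| 0.2 SD | 23% |
| 0.3 SD | 46% |
| 0.454 SD | 80% |
| 0.5 SD | 87% |

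The test responds in the same way to a prebiotic effect and to any other shared shift. The documents support no particular shift, so the table is illustration only.

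**3. The 80-value correlation with no association.** With two values per person and the same ICC in both variables, the variance of the sample correlation is inflated by about 1 + ICC². The actual error rate of a nominal 5% test is then 2 × [1 − Φ(1.96 / √(1 + ICC²))]:

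| ICC (both variables) | Inflation | Formula | Simulation, 20,000 runs |
|---|---|---|---|
| 0.5 | 1.25 | 8.0% | 8% |
| 0.7 | 1.49 | 10.8% | 11% |
| 0.9 | 1.81 | 14.5% | 15% |

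**4. Whether the named analyses reach the within-person link.** Simulation with 4,000 runs, assumed between-person SD 1.0 and within-person SD 0.5:

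| Truth | Paired t-test | 80-value correlation | Change-on-change |
|---|---|---|---|
| Within-person r = 0.6, no mean change, no between-person link | 5% | 25% | 99% |
| Between-person r = 0.5 only | 5% | 92% | 5% |

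In the first row the t-test is blind to the link and the pooled correlation mostly misses it. In the second row the pooled correlation correctly finds a between-person link, which says nothing about change within a person.

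**5. Power of a change-on-change regression, n = 40.** By simulation, one predictor gives 82%, 52% and 29% when it explains 19%, 10% and 5% of the variance in the observed change in k_el. The Fisher z formula gives 81%, 51% and 28%. With Bonferroni correction for 3, 5 or 10 tests, power at 19% is 68%, 61% or 52%.

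**6. What that regression cannot see.** Its intercept takes up any uniform shift, including a uniform prebiotic effect. If everyone's k_el rises by 0.454 SD and change in B is unrelated to change in k_el, the t-test has 80% power and the change slope is significant in 5%.

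**7. Stool intervals.** Trial 1 day 44 to day 74 is 30 days; adding about 120 days of washout gives about 150 days, or 143 if Trial 2 day −7 falls inside the washout. Day −7 to day 44 of Trial 2 is 51 days. Section 5B allows the day −7 stool on the day the prebiotic starts, and Section 5C allows it contemporaneously with supplementation. The first interval is therefore not always strictly prebiotic-free.

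**The case against.** The wording of the t-test is open. It is plural, and the sentence before it discusses detecting a two-day difference in half-life between two subjects. A slope comparison within each subject is conceivable and would fit the per-person prediction better. That stands as a reason to make the mean-change reading conditional. It does not fill the gap, because such comparisons would still not relate change in k_el to change in microbiota or demethylation.

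A reader might infer that the plan rules such an analysis out. It does not: the taxa sentence is loose enough to permit one. The supportable statement is that none is specified.

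A reader might also infer that the 80-value correlation is wrong in itself, or that a high rate of significance under a purely between-person link is an error rate. Neither follows. Secondary objective 1 seeks tools to assess an individual's metabolizing potential, and for that purpose differences between people are signal. The fault is limited to treating paired values as independent and to reading the result as within-person evidence.

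It is tempting to go further and claim that antibiotics bias the prebiotic comparison. Section 1D says elimination "is significantly slowed when taking antibiotics", which bears on use during a trial; Section 6 allows that use and requires it to be reported. The documents give no frequency, no size of effect and nothing on lingering effects of washout use, so no bias can be claimed.

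On importance, Section 2A says "This prebiotic is not the subject of this investigation in this study", Section 3C calls the study a pilot, Aim 1 needs fast and slow samples whatever produced them, and Aims 2 and 3 examine mechanism separately. All of that stands.

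**Conclusion.** The point holds in a limited form. Read as paired, the t-test estimates a mean difference between trials and cannot alone be attributed to the prebiotic. Under any reading of pairwise, no specified analysis tests the within-person link that Section 2A predicts. The 80-value correlation, if its values are treated as independent, has an error rate of about 8% to 15% over assumed ICCs of 0.5 to 0.9, instead of 5%. Its use for predicting k_el between people is legitimate.

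The plan's power figure is not in dispute. It carries over to a change analysis only if 19% refers to the observed change in k_el and one predictor is tested.

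A reader might infer that a change regression would establish a prebiotic effect. It would not: there is no concurrent group without prebiotic, and the slope shows association only.

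Importance is minor. The ICCs, SDs and shifts are assumptions. The mismatch between analysis and prediction rests on the text alone.

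**What to change.** In Section 11:

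(a) State that the t-test is paired, estimates Trial 2 minus Trial 1, and will not by itself be attributed to the prebiotic.

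(b) Add a regression of change in k_el on change in B_vivo, B_vitro and a short prespecified list of taxa (day 44 of Trial 2 minus day 44 of Trial 1), with multiplicity control. Report slopes as association. Note that the intercept absorbs any uniform shift, including a uniform prebiotic effect, so this complements the t-test and does not replace it. State that about 82% power needs 19% of the variance in the observed change explained by one predictor.

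(c) Analyse the 80 values with a subject random effect or subject-clustered standard errors, and separate between-person from within-person slopes.

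(d) Describe microbiota change from Trial 1 day 44 to Trial 2 day −7 beside the change from day −7 to day 44. Call the first interval near prebiotic-free only when the day −7 stool precedes the first dose. Note the unequal lengths and the different fish intake: no fish after the tuna meals in Trial 1, unrestricted in the washout.

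Optionally, repeat (a) and (b) without subjects who report antibiotic use during a trial. As a separate matter, the phone screen in Section 4A asks about antibiotics in the last month while Sections 3B and 6 exclude use within two months; these passages should be reconciled.

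Cost: text in Section 11 and a little more analysis. Hair and all three stools are already planned, so no visits, samples or subjects are added. The price is a weaker causal statement about the prebiotic.
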